5.2 DERIVATION RULES

5.2.1 AEs coding/grading

Adverse events are coded using the Medical dictionary for regulatory activities (MedDRA) terminology.

AEs will be assessed according to the Common Terminology Criteria for Adverse Events (CTCAE) version 4.03.

The CTCAE represents a comprehensive grading system for reporting the acute and late effects of cancer treatments. CTCAE grading is by definition a 5-point scale generally corresponding to mild, moderate, severe, life threatening, and death. This grading system inherently places a value on the importance of an event, although there is not necessarily proportionality among grades (a grade 2 is not necessarily twice as bad as a grade 1).

If CTCAE grading does not exist for an adverse event, the severity of mild, moderate, severe, and life-threatening, corresponding to Grades 1 - 4, will be used. CTCAE Grade 5 (death) will not be used in this study; rather, information about deaths will be collected through the EOT eCRF page

5.2.2 Study day

Definitions will be applied for all situations:

- Study day for post-treatment event = event date first dose date + 1
- Study day for pre-treatment event = first dose date event date

The first day of study drug is study day 1.

If duration is to be reported in weeks, duration in days will be divided by 7, likewise if in months, then duration in days will be divided by 30.4375 and if in years, duration in days will be divided by 365.25.

6 ANALYSIS POPULATIONS

6.1 RELEVANT PROTOCOL DEVIATIONS

Protocol deviations will be categorized and tabulated overall and by indication and formulation into the following categories per ICH guidelines for CSR-reportable protocol deviations:

- Patient developed study/treatment withdrawal criteria during the study, but was not withdrawn
- Patient received the wrong treatment or incorrect dose
- Patient took an excluded concomitant medication
- Patient did not satisfy the entry criteria

Other important deviations may also be identified and summarized, as necessary, which may impact the scientific value of the trial.

The main protocol deviations are listed in Attachment 8.1. Additional terms can be identified on the basis of the collected data during study.

All protocol deviations will be listed overall and by indication and formulation using Safety Set.

6.2 DEFINITION OF POPULATIONS FOR ANALYSIS

6.2.1 Full Analysis Set

Not applicable.

6.2.2 Safety Set

The Safety Set includes all patients who received at least one dose of study medication (Pasireotide) after enrolling into the roll-over protocol.

6.2.3 Subgroup of interest

Not Applicable

7 PLANNED ANALYSES

7.1 Analysis of the primary objective

The primary objective is to evaluate long term safety as assessed by the occurrence of AEs / SAEs.

7.1.1 Primary endpoint

The assessment of safety will be based mainly on the frequency and severity of AEs, AESI and SAEs. See also Section 7.4.1.

7.1.2 Statistical hypothesis, model, and method of analysis

The primary endpoint will be summarized descriptively overall and by indication and formulation and no formal analysis will be performed. No hypothesis will be tested.

7.2 Analysis of secondary efficacy objective(s)

The secondary objective of the study is to evaluate clinical benefit as assessed by the investigator.

7.2.1 Secondary endpoints

Proportion of patients with clinical benefit as assessed by the investigator will be summarized at scheduled visits. Clinical benefit will be summarized overall and by indication and formulation using the Safety Set.

7.3 EXTENT OF EXPOSURE

Definitions of duration of exposure, cumulative dose, average daily dose, actual dose intensity (DI), as well as intermediate calculations, include:

Pasireotide s.c.:

- Duration of exposure (days): min(last date of rollover study drug, date of death, date of data cut-off) first date of rollover study drug + 1
- Cumulative dose (μg): total dose of study drug taken by a patient in the rollover study
- Number of dosing days (days): duration of exposure number of zero dose days
- Average daily dose (μg/day): cumulative dose (μg) / number of dosing days (days)
- DI (µg/day): cumulative dose (µg) / duration of exposure (days)

Pasireotide LAR:

- Duration of exposure (months): (min(last date of rollover study drug+27, date of death, date of data cut-off) first date of rollover study drug + 1)/30.4375
- Cumulative dose (mg): total dose of study drug taken by a patient in the rollover study

- Number of dosing months (months): duration of exposure number of zero dose months
- Average monthly dose (mg/month): cumulative dose (mg) / number of dosing months (months)
- DI (mg/month): cumulative dose (mg) / duration of exposure (months)

Duration of exposure to study drug, average daily dose and DI will be summarized descriptively overall and by indication and formulation.

Summary of duration of exposure of study treatment in appropriate time units will include categorical summaries and continuous summaries (i.e. mean, standard deviation etc.) using appropriate units of time. The duration of exposure to study drug will be categorized into time intervals; frequency counts and percentages of patients with exposure in each time interval will be presented. The derived parameters above will also be listed overall and by indication and formulation using Safety Set.

Dose Changes

The number and percentage of patients with dose interruption, reduction and increase will be summarized overall and by indication and formulation in the safety set. Dose interruption, reduction and increase are defined as follows:

- **Interruption** is defined as any period of zero total daily dose followed by a non-zero dose.
- **Reduction** is defined as any decrease from the immediate prior non-zero total daily dose. Zero daily doses are not regarded as reductions.
- **Increase** is defined as any increase from the immediate prior non-zero total daily dose.

The number and percentage of patients with dose interruption, reduction and increase, along with reasons for dose change will be summarized overall and by indication and formulation using Safety Set.For the purpose of summarizing interruptions and reasons, in case multiple entries for interruption that are entered on consecutive days (for pasireotide s.c.) or on consecutive months (for pasireotide LAR) with different reasons will be counted as separate interruptions. However, if the reason is the same in this mentioned multiple entries on consecutive days or months, then it will be counted as one interruption. Listings of all doses of the study drug along with dose reduction, increase and interruption and reasons for dose change will be presented. The derived parameters above will also be listed overall and by indication and formulation using Safety Set.

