2.3 Rationale for dose and regimen selection

The selected doses and regimen will be based on the dose ranges and regimen available in the parent study. The starting dose of pasireotide alone or in combination with another treatment for Cushing's Disease and Acromegaly, should be the same dose as that which the patient was receiving in the parent study at roll over. After the starting dose, changes to pasireotide dose, and/or any medication given in combination with pasireotide for Cushing's Disease or Acromegaly, will be based on the investigator's judgment, but must follow the dose ranges provided in the parent study. Please note combination treatment in this rollover trial is only allowable for Cushing's Disease and Acromegaly parent protocols.

Pasireotide will be provided as:

1. Pasireotide s.c. – to be administered subcutaneously two or three times a day depending on the parent study dosing.
2. Pasireotide LAR to be administered as intramuscular injection every 28 days.

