10.4.2 Statistical hypothesis, model, and method of analysis

No hypothesis will be tested.

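### SAP 7.3 asks for overall average dose and dose intensity although s.c. is in µg/day and LAR in mg/month, and its daily-dose definition of interruption flags every on-schedule LAR patient with two or more injections

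*SAP*

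**What the plan says.** SAP 7.3 gives each formulation its own formulas. For s.c., duration is in days and both average daily dose and DI are in µg/day. The denominator of the average is "Number of dosing days (days): duration of exposure number of zero dose days" (read with a minus sign before the second term). For LAR, duration is in months and the dose measures are in mg/month:

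- "Number of dosing months (months): duration of exposure number of zero dose months" (again a difference)
- "Average monthly dose (mg/month): cumulative dose (mg) / number of dosing months (months"
- "DI (mg/month): cumulative dose (mg) / duration of exposure (months"

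The summary instruction then covers both formulations at once: "Duration of exposure to study drug, average daily dose and DI will be summarized descriptively overall and by indication and formulation". No conversion is stated. The average it names is the daily one, which exists only for s.c.

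The dose-change definitions in the same section are written once, for both formulations. An interruption "is defined as any period of zero total daily dose followed by a non-zero dose". Reduction and increase compare each dose with the last non-zero dose before it. A further rule, on merging several interruption entries, works in consecutive days for s.c. and consecutive months for LAR.

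Protocol 2.3 sets the LAR regimen: "Pasireotide LAR to be administered as intramuscular injection every 28 days". Protocol 4.1 and 7.1.3 allow ±7 days around the monthly LAR visit.

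**The concern.** Two instructions in SAP 7.3 give a wrong result for LAR if programmed as written.

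First, an overall mean of average dose or DI would combine a number in µg/day with a number in mg/month. The result has no unit. Because the s.c. numbers are far larger than the LAR numbers, it reacts mainly to how many patients are on each formulation.

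Second, a depot injection leaves almost every day with no dose given. A definition based on zero daily dose therefore treats the ordinary interval between two injections as an interruption.

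This is a long-term safety study, also classed as a voluntary PASS (Protocol 10.6). Its exposure and dose-change tables are what a reader uses to judge how much drug lies behind the adverse event results. Two programmers working from the same text could produce very different tables.

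**Working it through.** The plan states no figure on this point, so there is none to reproduce. The check applies the SAP 7.3 definitions to illustrative patients.

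**Inputs**
- From the documents: the 28-day LAR interval (Protocol 2.3), the ±7-day window (Protocol 4.1), 30.4375 days per month (SAP 5.2.2 and 7.3), and the formulas in SAP 7.3.
- Assumed: an s.c. patient on 600 µg b.i.d. with no zero-dose days; a LAR patient with 13 on-time injections of 40 mg; LAR shares of 20%, 50% and 80%.

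**1. Dose intensity per patient**
- s.c.: 2 × 600 = 1,200 µg/day.
- LAR: the last injection falls 12 × 28 = 336 days after the first. Duration = 336 + 27 + 1 = 364 days = 364 / 30.4375 = 11.96 months. Cumulative dose = 13 × 40 = 520 mg. DI = 520 / 11.96 = 43.48 mg/month.
- The same LAR course in the s.c. unit: 520,000 µg / 364 days = 1,428.6 µg/day.

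The two patients receive similar daily amounts but enter the overall mean as 1,200 and 43.48.

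**2. Overall mean**, with LAR share p: unconverted (1 − p) × 1,200 + p × 43.48; converted (1 − p) × 1,200 + p × 1,428.6.

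| LAR share | Unconverted (no unit) | Converted (µg/day) |
|---|---|---|
| 20% | 968.7 | 1,245.7 |
| 50% | 621.7 | 1,314.3 |
| 80% | 274.8 | 1,382.9 |

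As the LAR share rises, the unconverted figure falls steeply while the converted one rises a little. The unconverted figure also barely responds to the LAR dose. At a 50% share, changing LAR from 20 mg (21.74 mg/month) to 60 mg (65.22 mg/month) moves it from (1,200 + 21.74)/2 = 610.9 to (1,200 + 65.22)/2 = 632.6. Converted, the move is from (1,200 + 714.3)/2 = 957.1 to (1,200 + 2,142.9)/2 = 1,671.4 µg/day.

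**3. The unnamed LAR average.** If a programmer fills the gap by applying the s.c. average daily dose to LAR, only the 13 injection days count: 520 / 13 = 40 mg/day, or 40,000 µg/day. That is 28 times the 1,428.6 µg/day above.

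**4. Interruptions under the daily rule.** Between on-time injections, 27 of 28 days (96.4%) have zero dose. Anywhere in the permitted window (intervals of 21 to 35 days) there are 20 to 34 zero days.
- 13 on-time injections have 12 gaps, hence 12 interruptions. Counted per scheduled injection, the answer is 0.
- If one of the 13 is missed in mid-course, 12 are given, with 11 gaps and 11 interruptions. The per-injection answer is 1. Missing an injection lowers the literal count.
- Every LAR patient with at least two injections is flagged, so the percentage interrupted is 100% in that group.

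**5. Reductions and increases.** For a course of 40 mg × 4, 20 mg × 3, 40 mg × 6, the daily rule and the per-injection rule both give one reduction and one increase, because zero days are skipped in the comparison.

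**The case against.** The strongest reply is that SAP 7.3 already treats LAR separately and only the labels are loose. The LAR formulas are complete, and SAP 4.1 has all data summarised by indication and formulation, so LAR columns are planned and computable. Overall could mean across indications within one formulation. The LAR zero-dose unit is the month, and the rule for merging interruption entries also uses months, so a day-by-day reading was not intended.

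Part of this stands. A reader might infer that the exposure tables are meaningless for LAR; they are not, because the within-formulation LAR figures are well defined. A reader might also infer that all three dose-change definitions fail. Reduction and increase work for patients on LAR alone, as step 5 shows. A reader might expect a Cushing's disease column that mixes formulations, but that arises only if indication is not crossed with formulation, and SAP 4.1 reads naturally as a cross-classification. Nor do late injections go unseen. SAP 8.1 lists missed injections, intervals outside 28 ± 7 days, and intervals under 14 or over 56 days as deviations, SAP 6.1 tabulates deviations, and SAP 7.3 lists all doses.

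Two things do not fall away. SAP 4.2.1, 4.2.2, 7.1.2 and 7.2.1 use the same phrase, and there overall naturally means all patients; nothing in 7.3 says otherwise for dose. And the monthly wording shows the intention without changing the rule. The merging rule says how to count entries already classed as interruptions, not what makes a LAR interruption.

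**Conclusion.** The point holds in limited form. As written, overall average dose and DI combine incompatible units, the LAR average monthly dose is left out of the summary sentence, and the interruption definition gives a wrong result for LAR and conflicts with the monthly LAR unit used in the same section.

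The sizes above rest on the assumed doses, 13 on-time injections and LAR shares; other values change the figures but not the mixing of units. The interruption result needs only the 28-day regimen and a literal reading of the definition.

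The reach is narrow. A reader might infer that the safety conclusions are compromised, and the documents do not support that. The protocol says "No hypothesis will be tested", the primary endpoint is the frequency and severity of AEs and SAEs, and the AE incidence rules in SAP 7.4.1 use neither DI nor these dose-change definitions. What is affected is the descriptive exposure and dose-change tables: the overall dose columns and the LAR interruption counts.

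**What to change.** Revise SAP 7.3 in three places:

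- **Dose metrics.** Summarise cumulative dose, average dose and DI within formulation only (or within indication by formulation), or convert to one stated unit before pooling. Keep the overall summary for duration of exposure, in one time unit.
- **Summary sentence.** Name average monthly dose for LAR beside average daily dose for s.c.
- **Interruption.** For LAR, define it per scheduled injection: an injection recorded as zero or not given, followed by a non-zero injection. Keep the daily-dose definition for s.c. only.

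The LAR reduction and increase rules need no change. Delayed injections can stay with the protocol-deviation tables unless the sponsor chooses to state an interval threshold for this analysis.

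The cost is wording in one SAP section and the matching table shells, with no new data. SAP 2 has final-analysis decisions made before database lock, so the change belongs before then.

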7.4 SAFETY ANALYSIS

Safety analyses will be performed on Safety Set. The assessment of safety will be based mainly on the frequency of AEs, AESI and SAEs.

7.4.1 Adverse events (AEs)

Treatment emergent AEs are defined as those that started on or after the study medication, or those that started before study medication but worsened afterwards. AEs starting after 84 days following the last dose of pasireotide LAR treatment and after 30 days following the last dose of pasireotide s.c. treatment are not considered treatment emergent AEs. Summary tables for adverse events (AEs) have to include only AEs that started or worsened during the on-treatment period, the **treatment-emergent** AEs. However, all safety data

(including those from the post-treatment periods) will be listed and those collected during the post-treatment period are to be flagged.

The incidence of treatment-emergent adverse events (new or worsening from baseline) will be summarized by system organ class and/or preferred term, severity based on CTCAE grades (version 4.03), type of adverse event, relation to study treatment. The summary will include AEs regardless of study-drug relationship. The same analysis will be repeated for SAEs.

All treatment emergent AEs and SAEs will be listed. In this listing, the information on the relationship to study treatment will be included.

Adverse events will be coded using the Medical dictionary for regulatory activities (MedDRA) terminology using the latest available MedDRA version at the time of the analyses and the information of MedDRA version will be specified in the footnote of relevant outputs.

The following selection of AEs will be listed and summarized separately using Safety Set. AEs will be summarized for all grades and for grade 3 or 4 side-by-side.

- AEs
- SAEs
- AEs leading to study drug discontinuation
- AEs requiring dose adjustment or interruption
- AEs requiring additional therapy
- Adverse events of special interest (AESI)

For the legal requirements of ClinicalTrials.gov and EudraCT, two required tables on treatment- emergent adverse events which are not serious adverse events with an incidence greater than 5% and on treatment-emergent serious adverse events and SAE suspected to be related to study treatment will be provided by system organ class and preferred term on the safety set population.

If for a same patient, several consecutive AEs (irrespective of study treatment causality, seriousness and severity) occurred with the same SOC and PT:

- A single occurrence will be counted if there is ≤ 1 day gap between the end date of the preceding AE and the start date of the consecutive AE
- More than one occurrence will be counted if there is > 1 day gap between the end date of the preceding AE and the start date of the consecutive AE

For occurrence, the presence of at least one SAE / SAE suspected to be related to study treatment / non SAE has to be checked in a block e.g., among AE's in a \leq 1 day gap block, if at least one SAE is occurring, then one occurrence is calculated for that SAE.

The number of deaths resulting from SAEs suspected to be related to study treatment and SAEs irrespective of study treatment relationship will be provided by SOC and PT.

Adverse events of special interest / grouping of AEs

The specific categories of AEs of special interest list for SOM230 are listed in attachment 8.2.

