- Women are considered post-menopausal and not of child bearing potential if they have had 12 months of natural (spontaneous) amenorrhea with an appropriate clinical profile (i.e. age appropriate, history of vasomotor symptoms) or have had surgical bilateral oophorectomy (with or without hysterectomy), total hysterectomy, or tubal ligation at least six weeks ago. In the case of oophorectomy alone, only when the reproductive status of the woman has been confirmed by follow up hormone level assessment is she considered not of child-bearing potential.
- Sexually active males unless they use a condom during intercourse while taking drug and for 1 months after pasireotide s.c. last dose and 3 months after pasireotide LAR last dose and should not father a child in this period. A condom is required to be used also by vasectomized men in order to prevent delivery of the drug via seminal fluid.

If a study patient or partner becomes pregnant or suspects being pregnant during the study treatment or within 1 month after the final dose of pasireotide s.c. or 84 days after the final dose of pasireotide LAR, the Study Doctor needs to be informed immediately and ongoing study treatment with pasireotide has to be stopped immediately. For patients taking pasireotide LAR, the future dose injections will be cancelled.

6 Treatment

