8.2 Serious adverse events

8.2.1 Definitions

Serious adverse event (SAE) is defined as one of the following:

- Is fatal or life-threatening
- Results in persistent or significant disability/incapacity
- Constitutes a congenital anomaly/birth defect
- Is medically significant, i.e., defined as an event that jeopardizes the patient or may require medical or surgical intervention to prevent one of the outcomes listed above
- Requires inpatient hospitalization or prolongation of existing hospitalization,
- Note that hospitalizations for the following reasons should not be reported as serious adverse events:
 - Routine treatment or monitoring of the studied indication, not associated with any deterioration in condition
 - Elective or pre-planned treatment for a pre-existing condition that is unrelated to the indication under study and has not worsened since signing the informed consent
 - Social reasons and respite care in the absence of any deterioration in the patient's general condition
- Note that treatment on an emergency outpatient basis that does not result in hospital admission and involves an event not fulfilling any of the definitions of a SAE given above is not a serious adverse event

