8.2.2 Reporting

To ensure patient safety, every SAE, regardless of suspected causality, occurring after the patient has provided informed consent and until at least 30 days for patients on the s.c formulation and 84 days for patients on the LAR formulation after the patient has stopped study treatment must be reported to IQVIA Safety office within 24 hours of learning of its occurrence. IQVIA, in its turn, will promptly inform Recordati.

Any SAE that begins or worsens after signing of the informed consent for the roll-over and during the safety follow up period defined in the parent protocol should be reported as an adverse event in both clinical databases; however, only one SAE report will be sent to IQVIA.

- Any SAE that begins or worsens **during** the safety follow-up period specified in the parent study should have an SAE report submitted to IQVIA—with the parent protocol study number.
- Any SAE that begins or worsens **after** the safety follow-up period specified in the parent study should have an SAE report submitted to IQVIA with the roll-over protocol study number.

Any additional information for the SAE including complications, progression of the initial SAE, and recurrent episodes must be reported as follow-up to the original episode within 24 hours of the investigator receiving the follow-up information. An SAE occurring at a different time interval or otherwise considered completely unrelated to a previously reported one should be reported separately as a new event.

The date of the informed consent signed for this roll-over study (the roll-over date) is important to determine how SAEs should be reported:

- Any SAEs occurred prior to that date should be reported for the parent protocol, including all the follow up information relevant to such SAEs.
- New SAEs with an onset date after the roll-over date will be reported for this protocol.

It is important to use the right SAE form with the correct protocol number for these two scenarios, to avoid confusion in SAE processing. For a patient already on the roll-over protocol but follow up information is reported for the previous SAEs in the parent protocol, it must be clearly labeled that this is for the parent protocol number.

Any SAEs experienced after the 30 day/84 day safety evaluation follow-up period (or 5 half-lives, if half-life is established, whichever is longer) should only be reported to IQVIA if the investigator suspects a causal relationship to the study treatment.

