8.4 Pregnancies

To ensure patient safety, each pregnancy occurring while the patient is on study treatment must be reported to IQVIA within 24 hours of learning of its occurrence. IQVIA, in its turn, will promptly inform Recordati. The pregnancy should be followed up to determine outcome, including spontaneous or voluntary termination, details of the birth, and the presence or absence of any birth defects, congenital abnormalities, or maternal and/or newborn complications.

Pregnancy should be recorded on a Clinical Trial Pregnancy Form and reported by the investigator to IQVIA. Pregnancy follow-up should be recorded on the same form and should include an assessment of the possible relationship to the study treatment any pregnancy outcome. Any SAE experienced during pregnancy must be reported on the SAE Report Form.

The protocol must specify how long the newborn will be followed up (just birth, or xyz months). Further advice on the length of post-natal follow up can be sought from Recordati and should be driven by the type of congenital abnormality expected.

Pregnancy outcomes must be collected for the female partners of any males who took study treatment in this study. Consent to report information regarding these pregnancy outcomes should be obtained from the mother.

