CSOM230C1202	86	Acromegaly or pituitary	Acromegaly
CSOM230C2402	87	Acromegaly	Acromegaly
CSOM230X2404	115	Melanoma	Other diseases
CSOM230X2404	116	Melanoma	Other diseases
CSOM230C2413	117	Acromegaly	Acromegaly
CSOM230B2411	125	Cushing's disease	Cushing's disease
CSOM230XDE04	126	Prostate cancer	Other diseases
CSOM230D2401	136	Pituitary adenomas	Other diseases
CSOM230DIC03	137	NET	Other diseases

Table 2-1 Derivation of the indication information – Part 1

Table 2-2Derivation of the indication information – Part 2

Parent study number	eCRF code	Parent data set	Parent data set variable	Indication	Indication group
CSOM230C2110E1 CSOM230C2110E1 CSOM230B2219	80 80 114 or 113	ADMG ADMG AIDENT	CLIND CLIND DISTYP3A	Carcinoid Acromegaly Acromegaly	Other diseases Acromegaly Acromegaly
CSOM230B2219	114 or 113	AIDENT	DISTYP3A	Cushing's disease	Cushing's disease

Treatment period

The overall observation period will be divided into two mutually exclusive segments:

on-treatment period: from day of first dose of study medication in the roll-over study to 3 months (84 days) following the last dose of pasireotide LAR treatment and to 1 month (30 days) following the last dose of pasireotide s.c. treatment.

post-treatment period: starting at 3 months+1 day (day 85) following the last dose of pasireotide LAR treatment and at 1 month+1 day (day 31) following the last dose of pasireotide s.c. treatment.

Safety summaries (tables, figures) include only data from the on-treatment period. In addition, a separate summary for death including on treatment and post treatment deaths will be provided. In particular, summary tables for adverse events (AEs) will summarize only on-treatment events, with a start date during the on-treatment period (treatment-emergent AEs).

However, all safety data (including those from the post-treatment period) will be listed and those collected during the post-treatment period will be flagged.

Study Treatment

Study drug and investigational treatment refer to pasireotide. Patients are to use the study treatment based on the parent protocol.

Date of first/last administration of study drug

The start date of study drug is defined as the first date when a non-zero dose of study drug was administered in the roll-over study and recorded on the Dosage Administration Record (DAR) eCRF.

The date of last administration of study drug is defined as the last date when a non-zero dose of study drug was administered and recorded on DAR eCRF.

Laboratory data

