Pregnancy tests will be listed overall and by indication and formulation.

4.2 *Patient disposition, demographics and other baseline characteristics*

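### A congenital anomaly first dated at a term birth falls outside the SAP's 30/84-day onset window, so it is missing from the SAE tables, and no pregnancy-outcome output is planned

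*SAP*

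**What the plan says.** **SAP.** Section 7.4.1 sets treatment emergence by start date. For the long-acting formulation, "AEs starting after 84 days following the last dose of pasireotide LAR treatment" are excluded; for the subcutaneous one, those starting "after 30 days following the last dose of pasireotide s.c. treatment are not considered treatment emergent AEs". Section 4.1 applies the same limit to all tabular output: "Safety summaries (tables, figures) include only data from the on-treatment period". Later safety data are listed and flagged. Deaths are the one stated exception, with a summary that includes post-treatment deaths (4.1, 7.4.2). The only pregnancy output is in 4.1: "Pregnancy tests will be listed overall and by indication and formulation". The Safety Set contains patients dosed in the roll-over study (6.2.2).

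**Protocol.** One SAE criterion in 8.2.1 is that the event "Constitutes a congenital anomaly/birth defect". Section 8.4 follows pregnancies to outcome, including "the presence or absence of any birth defects, congenital abnormalities, or maternal and/or newborn complications", and asks for outcomes in female partners of male patients, with the mother's consent. Section 7.1.4 requires monthly home urine tests during treatment and the 30/84-day follow-up, and sends any positive result to 8.4. Section 5.3 says that on a known or suspected pregnancy "ongoing study treatment with pasireotide has to be stopped immediately". Section 8.2.2 says that SAEs after the follow-up period "should only be reported to IQVIA if the investigator suspects a causal relationship to the study treatment".

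**The concern.** An onset window after the last dose suits events that arise in the patient while drug is present or washing out. It does not suit fetal harm. There the relevant time is exposure at conception or in early pregnancy, whereas the finding may first be dated at delivery. If dosing stops at detection, delivery at term comes months later, and the rule labels an exposed outcome as post-treatment.

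Long-term safety is the primary objective, and the study is run as a voluntary post-authorisation safety study. Protocol 1.1.1 describes Cushing's disease, one of the main indications, as affecting mostly women and mostly adults aged 20 to 50. Protocol 11.3 tells women that fetal risk is unknown. Someone who relies on the SAE summary tables would not see an anomaly of this kind, and no other planned output reports pregnancy outcomes.

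**Working it through.** The plan gives no figure to reproduce beyond the windows themselves, so the check is date arithmetic.

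**Inputs from the documents**
- Window W after last dose: 30 days (s.c.), 84 days (LAR) (SAP 7.4.1).
- Dosing stops when pregnancy is known or suspected (Protocol 5.3).
- Home tests are monthly for women of childbearing potential (Protocol 7.1.4).

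**Assumptions not in the documents**
- Conception is at gestational day 14, and term is 37 to 42 weeks. Birth day B after conception is then 37 × 7 − 14 = 245 to 42 × 7 − 14 = 280.
- A urine test is positive from about day 14 after conception. Monthly testing then detects by about day 14 + 30 = 44, so the last-dose day L is at most 44.
- The onset of an anomaly is dated at birth. Neither document defines this date.

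**Formulas.** Last dose to birth = B − L. Days past the window = B − L − W.

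**Dosing stopped by day 44**
- Last dose to birth: 245 − 44 = 201 to 280 − 44 = 236 days.
- Past the s.c. window: 201 − 30 = 171 to 236 − 30 = 206 days.
- Past the LAR window: 201 − 84 = 117 to 236 − 84 = 152 days.

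**L varied over days 0 to 90** (this also allows for later recognition, as may happen with partner pregnancies, which the home tests do not cover)
- s.c.: 245 − 90 − 30 = 125 to 280 − 0 − 30 = 250 days too late.
- LAR: 245 − 90 − 84 = 71 to 280 − 0 − 84 = 196 days too late.

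**How late dosing must continue for a term birth to fall inside the window** (L = B − W)
- s.c.: day 245 − 30 = 215 for birth at 37 weeks, day 280 − 30 = 250 at 42 weeks.
- LAR: day 245 − 84 = 161 at 37 weeks, day 280 − 84 = 196 at 42 weeks.

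**What the window can still admit.** With L = 44 it closes at (44 + 30 + 14) / 7 = 12.6 weeks' gestation (s.c.) or (44 + 84 + 14) / 7 = 20.3 weeks (LAR). A miscarriage before then, reported as the patient's own SAE, is tabulated. For LAR, an anomaly dated from a scan up to about 20 weeks could also be inside.

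**Two further gaps, independent of the window**
- Newborns and untreated partners are not in the Safety Set, and neither document says whether a child's event is counted on the parent's record. A wider window alone would not bring their events into the tables.
- The final analysis is triggered by 84 or 30 days of follow-up (SAP 4.1), so it can precede a delivery. Newborn follow-up in protocol 8.4 is still unfilled template text.

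**The case against.** **A reader might infer that the tables will show no fetal harm by construction.** The documents do not support that. Early losses and prenatal diagnoses inside the window can be tabulated. So can a birth where dosing continued: protocol 7.1.5.1 lists pregnancy among reasons for which a patient may be withdrawn, and SAP 8.1 has a deviation code (D04) for a patient who became pregnant and was not withdrawn. The onset date of an anomaly is undefined, and late events are listed and flagged. What stands is narrower: a birth-dated anomaly at term, with dosing stopped at detection, is absent from the tables.

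**A reader might also infer that 8.2.2 causes late anomalies to go unreported.** That is one reading and not a demonstrated loss. Section 8.4 asks for follow-up to outcome with a relationship assessment, and for SAEs during pregnancy on the SAE form, with no day-30/84 or causality limit. The two sections sit uneasily together, and neither says which governs.

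**Materiality.** Pregnant women are excluded, highly effective contraception is required, the analysis is descriptive, and the number of pregnancies is unknown. For rare events a listing may suffice. That argues against forcing these events into incidence tables. It does not justify having no outcome output, because the one listing planned for pregnancy covers test results only.

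**Conclusion.** The point holds in limited form. When dosing stops at detection, an anomaly first dated at a term birth misses the s.c. window by 171 to 206 days and the LAR window by 117 to 152 days. It still misses them by at least 125 and 71 days if the last dose is as late as day 90 after conception. It is then absent from every SAE summary table and appears at most in a listing, flagged post-treatment. The SAP plans no output for the outcomes that protocol 8.4 collects.

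This rests on birth-dated onset, the assumed conception and detection dates, and the stopping instruction in 5.3. How many events are affected cannot be stated, because the documents give no pregnancy count. The change should be made: the rule misclassifies an SAE type that the protocol itself names, and the data are already required.

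**What to change.** **SAP 7.4.** Add a separate pregnancy-outcome count and listing, outside the 30/84-day onset window, for patients and for partners where consent is given. For each pregnancy:
- classify exposure by estimated conception date relative to last dose;
- show formulation, outcome and any congenital anomaly;
- link the record to the parent patient;
- show pregnancies unresolved at cut-off as ongoing.

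Do not merge newborn or partner events into the Safety Set SAE incidence tables, whose denominator is dosed patients. Footnote those tables to refer to the pregnancy output.

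**Protocol 8.2.2.** State that pregnancy-outcome SAEs follow 8.4 and are not subject to the causality filter after day 30/84.

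**Reconcile.** Protocol 5.3 requires treatment to stop at once on pregnancy, whereas 7.1.5.1 says only that the patient may be withdrawn. The two must be brought into agreement; this review takes no position on which is right.

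**Cost.** One small extra output and one sentence in 8.2.2. Protocol 7.1.4 and 8.4 already require pregnancies, including those found by tests during the follow-up period, to be followed to outcome. Partner records will be incomplete where consent is refused, and the safety picture may look less favourable.
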